### 5.4.2. Local Tolerability

Tolerability will be assessed with the following skin irritation scoring system, where the score consists of a numeric score according to the dermal response scoring i), and a letter according to the other effects scoring ii), as follows:

i) Dermal response scoring:

- 0 = no evidence of irritation
- 1 = minimal erythema, barely perceptible (pink)
- 2 = moderate erythema (definite redness), readily visible; minimal edema or minimal papular response
- 3 = strong erythema (intense redness), or erythema and papules
- 4 = definite edema
- 5 = erythema, edema, and papules
- 6 = vesicular eruption
- 7 = strong reaction spreading beyond test site

ii) Other effects:

- Z = no other effect
- A = slight glazed appearance
- B = marked glazing
- C = glazing with peeling and cracking
- F = glazing with fissures
- G = film of dried serous exudate covering all or part of the dose site
- H = small petechial erosions and/or scabs

### 5.4.3. Safety Related Study Specific Dose Adjustment Criteria

If AEs are of severe intensity and are similar across subjects, or if unacceptable pharmacological effects, reasonably attributable in the opinion of the investigator to dosing with GSK2646264, or if dose limiting toxicity (see Section 5.4.1), are observed in at least 2 subjects, relevant reporting and discussion with the GSK medical monitor and the SRT will take place.

If a Serious Adverse Event (SAE) occurs in 1 subject and is deemed to be drug related, this would be deemed an SAR (Serious Adverse Reaction), and dosing will be halted in the individual (Relevant reporting and discussion with the GSK medical monitor and the SRT will take place, and halting of dosing will be considered for all study subjects). If dosing is halted for the entire study, any resumption of dosing will only take place after consideration by the SRT and discussion with the investigators and may necessitate approval of a substantial amendment submitted to the Ethics committees and Regulatory authorities.

[figure not shown]
If average predicted or observed  $C_{max}$  or  $AUC(0-24\text{ h}$  after last dose) of GSK264624 is greater than 16 ng/mL or 220 ng.hr/mL, respectively, subsequent doses may be adjusted based on toxicology cover and this will be agreed by the SRT.

#### 5.4.4. Liver Chemistry Stopping Criteria

**Liver chemistry stopping and increased monitoring criteria** have been designed to assure subject safety and evaluate liver event etiology (in alignment with the FDA premarketing clinical liver safety guidance).

<http://www.fda.gov/downloads/Drugs/GuidanceComplianceRegulatoryInformation/Guidances/UCM174090.pdf>

## Phase II Liver Chemistry Stopping and Increased Monitoring Algorithm

Liver Safety Required Actions and Follow up Assessments Section can be found in Section [12.2](#).

#### 5.4.4.1. Study Treatment Restart or Rechallenge

If subject meets liver chemistry stopping criteria do not restart/rechallenge subject with study treatment unless:

- GSK Medical Governance approval is granted
- Ethics and/or IRB approval is obtained, if required, and

- Separate consent for treatment restart/rechallenge is signed by the subject

Refer to Section [12.2](#) for full guidance.

#### 5.4.5. QTc Stopping Criteria

A subject that meets either criterion below will be withdrawn from the study. The same QT correction formula (e.g QTcF) should be used to determine inclusion and discontinuation for any individual subject throughout the study.

- QTcF > 500 msec,
- Change from baseline: QTcF > 60 msec

If a subject has underlying bundle branch block the following withdrawal criteria should be used instead:

Baseline QTcF value (with underlying bundle branch block)	QTcF withdrawal criteria
<450 msec	>500 msec
450-480 msec	≥530 msec

Withdrawal of subjects is to be based on an average QTcF value of triplicate ECGs. If an ECG demonstrates a prolonged QT interval, then obtain 2 more ECGs over a brief period of time and then use the averaged QTcF values of the 3 ECGs to determine whether the subject should be discontinued from the study.

#### 5.5. Subject and Study Completion

A completed subject will be defined as a subject who receives at least 25 days of study drug and completes the end of treatment biopsy and assessment. Patients will be followed as per the Time & Events table, Section [7.1](#) until complete resolution of induced PV lesions.

The end of the study is defined as the last subject's last visit.

### 6. STUDY TREATMENT

The term 'study treatment' is used throughout the protocol to describe any combination of products received by the subject as per the protocol design. Study treatment may therefore refer to the individual study treatments or the combination of those study treatments.

Study Treatment		
Product name:	1% GSK2646264	Placebo
Formulation description:	White to off white aqueous cream	White to off white aqueous cream
Dosage form:	Topical	Topical
Unit dose strength(s)/Dosage level(s):	1% (w/w)	NA
Route/ Administration/ Duration:	Topical	Topical
Dosing instructions:	Should be applied topically as directed.	Should be applied topically as directed.
Physical description:	White-to-off-white aqueous cream stored in amber glass jars	White-to-off-white aqueous cream stored in amber glass jars
Manufacturer/ source of procurement:	Medpharm Guildford	Medpharm Guildford

[figure not shown]
## 6.1. Treatment Assignment

Subjects will be assigned to treatment in accordance with the randomisation schedule generated by Clinical Statistics, prior to the start of the study, using validated internal software.

Skin areas A-C in group A are horizontally distributed across the back of the patient. The PV lesions will be labelled A, B, C. Study drug and placebo will be randomly assigned to lesions A and C. Lesion B will not be assigned a treatment and will be used for the baseline skin biopsy. A further area of uninvolved skin (area D) will also be treated with study drug or placebo in a ratio of 4:1. Another area of uninvolved skin (area E) will not be treated with either study drug or placebo and will be used solely to take a baseline biopsy.

Lesion/Skin Area	Type	Biopsy timing	Receives Drug/Placebo
A	PV lesion	Day 28	✓
B	PV lesion	Baseline	
C	PV lesion	Day 28	✓
D	Uninvolved Skin	Day 28	✓
E	Uninvolved Skin	Baseline	

**Figure 1 Approximate anatomical representation of UV lesion induction sites (A-C) and uninvolvled skin (D and E) for Group A**

Group A subjects will be assigned to the following regimens:

	Skin Sites A/C/D	Assignment ratio
Sequence 1	A/P/A	4
Sequence 2	A/P/P	1
Sequence 3	P/A/A	4
Sequence 4	P/A/P	1

P=Placebo, A= GSK2646264 1%

The nurse administering the treatments may be aware whether a patient is assigned to sequences 1/4 or sequences 2/3, however they will remain blinded to treatment.

In group B, at the day -5 to day -3 visit, prior to pre-dose biopsies being taken, the two chosen lesions will be labelled F and G based on size (F >G). The two lesions will be randomly assigned placebo or study drug. An area of uninvolvled skin (area H) will not

be treated with either study drug or placebo and will be used solely to take a biopsy at baseline. These lesions can be on any part of the body (all 3 lesions must be in the same anatomical area), but the subject must consent to be biopsied from the area with the lesions.

Lesion/Skin Area	Skin Type	Biopsy timing	Receives Drug/Placebo
F	Natural lesion	Baseline and Day 28	✓
G	Natural lesion	Baseline and Day 28	✓
H	Uninvolved Skin	Baseline	

Group B subjects will be assigned to one of the following regimens:

	Skin Sites F/ G	Assignment ratio
Sequence 1	A/P	1
Sequence 2	P/A	1

P=Placebo, A= GSK2646264 1%

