## **6.5. Compliance with Study Treatment Administration**

When subjects are dosed at the site or at their home, they will receive study treatment directly from the investigator or designee which may include a study nurse. The date and time of each dose administered in the clinic or at the subjects home will be recorded in the source documents.

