Procedure	Screening (up to Day - 28)	Day -15	Day -14	Day - 13 to - 1	Day 1	Day 2 to Day 13	Day 14	Day 15 to Day 20	Day 21 to Day 27	Day 28	Day 29 to 42	Follow- up a	a All procedures listed to also be conducted if a subject decides to prematurely withdraw/discontinue
Lesion induction assessment			<----X---->										
Lesion resolution assessment											X	X	
Clinical score				X		X				X			Components of the RCLASI as defined in Section 7.3 Assessments to be performed pre-dose
Local Tolerability Assessment				X	X	X	X	X	X	X			Assessments to be performed pre-dose and up to one hour following dosing on days of dosing
Dosing				X	X	X	X	X	X	X			Once daily
Randomisation				X									Pre-dose

Procedure	Screening (up to Day - 28)	Day -15	Day -14	Day - 13 to - 1	Day 1	Day 2 to Day 13	Day 14	Day 15 to Day 20	Day 21 to Day 27	Day 28	Day 29 to 42	Follow- up a	a All procedures listed to also be conducted if a subject decides to prematurely withdraw/discontinue
PK blood sample					X	X	X		X	X	X	X	Sampling timepoints: Day 1 = pre-dose; and 5hrs ( $\pm 1$ hr)  Between Day 2 and Day13: one pre-dose sample or postdose sample with time recorded since last dose  Day 14: predose sample  Between Day 21 and Day27: one pre-dose sample or postdose sample with time recorded since last dose  Day 28: one postdose sample with time recorded since last dose  Between Day 29 and Day 42: one sample with time recorded since last dose  Follow-up visit: one sample with sampling day recorded
AE/SAE Review	X								X				
Concomitant Medication Review	X								X				

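### Protocol 6.1 says the Group A nurse stays blinded while knowing the sequence pair, but with 4:1 allocation at site D the pair marks one lesion as active with 80% probability, so the nurse is only partly blinded

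*Protocol*

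**What the plan says.** Protocol 6.1 assigns each Group A patient one of four sequences over three treated sites: photoprovoked lesions A and C, and uninvolved skin D. The table rows, in site order A/C/D with the allocation weight last, are "Sequence 1 A/P/A 4", "Sequence 2 A/P/P 1", "Sequence 3 P/A/A 4" and "Sequence 4 P/A/P 1". The same section explains the weights: "A further area of uninvolved skin (area D) will also be treated with study drug or placebo in a ratio of 4:1". Sections 4.1 and 4.2 repeat the 4:1 ratio, and SAP 2.3 repeats the sequence table.

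Below the table, 6.1 states that the nurse administering treatment "may be aware whether a patient is assigned to sequences 1/4 or sequences 2/3, however they will remain blinded to treatment". Section 6.2 describes the study as double blind, with only the sponsor unblinded.

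Two other places bear on the consequence. On dosing, in the clinic or at home, section 6.5 says of patients that "they will receive study treatment directly from the investigator or designee which may include a study nurse". For local tolerability, the Group A Time and Events table (7.1.1) says: "Assessments to be performed pre-dose and up to one hour following dosing on days of dosing".

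**The concern.** The sentence in 6.1 discloses something to the nurse and then says that the disclosure is harmless. It would be harmless if site D were allocated 1:1. At 4:1 it is not, because the pair ties site D, whose treatment is strongly predictable, to one of the two lesions being compared.

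Lesions A and C are Group A's within-patient comparison of drug with placebo. Both the RCLASI components and local tolerability are graded by looking at the skin, and local tolerability also enters the dose-limiting toxicity definition in 5.4.1. A grader with good grounds to believe which lesion is active could shift either score. Whether any grader would be in that position depends on who does the scoring, which the plan leaves open.

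**Working it through.** **Inputs.** The four sequences and their weights (4, 1, 4, 1; total 10), and the pair the nurse may know (1/4 or 2/3), all from Protocol 6.1. The planned number, up to 5 randomised, is from Protocol 9.2.

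**Step 1: reproduce the plan's own figures.**
- P(D active) = (4 + 4)/10 = 0.80, which is the stated 4:1.
- P(lesion A active) = (4 + 1)/10 = 0.50, and the same for lesion C.

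The table is internally consistent.

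**Step 2: what the pair reveals.**

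| Sequence | A | C | D | Weight | Lesion matching D |
|---|---|---|---|---|---|
| 1 | active | placebo | active | 4 | A |
| 4 | placebo | active | placebo | 1 | A |
| 2 | active | placebo | placebo | 1 | C |
| 3 | placebo | active | active | 4 | C |

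Pair 1/4 means that D shares lesion A's cream; pair 2/3 means that D shares lesion C's cream.

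**Step 3: condition on the pair.**
- P(A active | pair 1/4) = 4/(4 + 1) = 0.80
- P(C active | pair 2/3) = 4/(1 + 4) = 0.80

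Each pair has probability 5/10, so the best guess is right with probability 0.80 overall, against 0.50 without the pair. The pair adds nothing about site D itself: P(D active) stays 0.80 within each pair. The leak concerns lesions A and C only.

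**Step 4: dependence on the ratio.** With r:1 at site D, the best guess is right with probability r/(r + 1): 50% at 1:1, 67% at 2:1, 75% at 3:1, 80% at 4:1.

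**Step 5: over the planned group.** This assumes exactly 5 patients and independent allocations; the plan says up to 5 and gives no block size.

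| | Pair known (p = 0.8) | Pair unknown (p = 0.5) |
|---|---|---|
| Expected correct guesses, 5p | 4.0 | 2.5 |
| P(at least 4 of 5) = 5p⁴(1 − p) + p⁵ | 0.410 + 0.328 = 0.737 | 6/32 = 0.188 |
| P(all 5) = p⁵ | 0.328 | 0.031 |

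**The case against.** The strongest reply concerns consequence, not arithmetic, and much of it stands.

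- **The nurse does not know the assignment.** The protocol says only that the nurse may know the pair, and one guess in five is still wrong. A reader might infer that the nurse is unblinded; the table supports only partial blinding.
- **The double-blind label.** A reader might infer that it fails for Group A as a whole. The documents do not support that. Pair knowledge is attributed to the administering nurse alone. Section 6.5 lets an investigator apply the cream, but nothing says that an investigator would learn the pair.
- **Biased endpoints.** A reader might infer that whoever applies the cream also grades the skin, because tolerability is scored around each dose and doses may be given at home. That is a guess from timing. Section 5.4.2 gives the tolerability scale and 7.3 the RCLASI components, and neither names an assessor. The guess is weaker still for RCLASI, which is scored before dosing at a few scheduled visits.
- **Little weight in this trial.** Group A was planned at up to 5 randomised patients, and the synopsis plans a descriptive summary for it. SAP 2.1 says that none was randomised and that no outputs will be generated for this part. Group B has two sequences at 1:1 and no third treated site, so the mechanism cannot arise there.

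None of this rescues the sentence itself. The 4:1 ratio is printed in the protocol, and no section withholds it from site staff, acknowledges the inference or adds a safeguard.

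**Conclusion.** The blinding statement in Protocol 6.1 is wrong as written. For a nurse who knows the sequence pair and the printed ratio, the lesion sharing site D's cream is active with probability 80% instead of 50%, so that nurse is only partly blinded as to lesions A and C. This follows from the allocation table with no further assumption.

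Bias in the A versus C comparison is conditional: it needs the person applying the cream, or someone that person informs, to score local tolerability or RCLASI. The plan neither says this happens nor rules it out.

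Severity is minor. The defect lies in the protocol's description of Group A and would carry into any re-use of this photoprovocation design. It changes no reported result.

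**What to change.** **Preferred.** Supply sites A, C and D from three separately coded, identical containers per Group A patient, with codes that do not show which two hold the same cream. The pair is then never visible and the best guess returns to 50%. Keep the 4:1 ratio and the sequence table, and delete the sentence in 6.1.

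**If that cannot be supplied.** Reword 6.1 to say that the nurse is partly blinded as to lesions A and C. State that the person applying the cream does not score local tolerability or RCLASI, where existing site staff allow.

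**Cost.** Probably one more labelled container per Group A patient. This assumes two at present: the documents do not give the number, and Protocol 6.4 leaves further preparation detail to the Study Reference Manual. SAP 11.3.2 records container weight before and after each application, so an extra container also adds its own daily weighings: at most 5 patients × 28 days = 140 before-and-after pairs. The allocation and the analysis do not change. The fallback needs only wording and a division of tasks at the site.

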## 6.2. Blinding

This will be a double blind (sponsor unblinded) study and the following will apply.

- The investigator or treating physician may unblind a subject's treatment assignment **only in the case of an emergency** OR in the event of a serious medical condition when knowledge of the study treatment is essential for the appropriate clinical management or welfare of the subject as judged by the investigator.
- Investigators have direct access to the subject's individual study treatment.
- It is preferred (but not required) that the investigator first contacts the Medical Monitor or appropriate GSK study personnel to discuss options **before** unblinding the subject's treatment assignment.
- If GSK personnel are not contacted before the unblinding, the investigator must notify GSK as soon as possible after unblinding, but without revealing the treatment assignment of the unblinded subject, unless that information is important for the safety of subjects currently in the study.
- The date and reason for the unblinding must be fully documented in the CRF

A subject may continue in the study if that subject's treatment assignment is unblinded.

- GSK's Global Clinical Safety and Pharmacovigilance (GCSP) staff may unblind the treatment assignment for any subject with an SAE. If the SAE requires that an expedited regulatory report be sent to one or more regulatory agencies, a copy of the report, identifying the subject's treatment assignment, may be sent to investigators in accordance with local regulations and/or GSK policy.

## 6.3. Packaging and Labeling

The contents of the label will be in accordance with all applicable regulatory requirements.

## **6.4. Preparation/Handling/Storage/Accountability**

A description of the methods and materials required for preparation of GSK2646264 is given below. More details will be available for sites to use in the Study Reference Manual (SRM).

- Only subjects enrolled in the study may receive study treatment and only authorized site staff, which may include a study nurse, may supply or administer study treatment. All study treatments must be stored in a secure environmentally controlled and monitored (manual or automated) area in accordance with the labelled storage conditions with access limited to the investigator and authorized site staff which may include a study nurse.
- The investigator, institution, or the head of the medical institution (where applicable) is responsible for study treatment accountability, reconciliation, and record maintenance (i.e. receipt, reconciliation and final disposition records).
- Further guidance and information for final disposition of unused study treatment are provided in the SRM.
- Under normal conditions of handling and administration, study treatment is not expected to pose significant safety risks to site staff which may include a study nurse. Adequate precautions to avoid direct eye or skin contact should be taken. In the case of unintentional occupational exposure notify the monitor, Medical Monitor and/or GSK study contact.
- A Material Safety Data Sheet (MSDS)/equivalent document describing occupational hazards and recommended handling precautions either will be provided to the investigator, where this is required by local laws, or is available upon request from GSK.

In the case of unintentional occupational exposure notify the monitor, Medical Monitor and/or GSK study contact.

## **6.5. Compliance with Study Treatment Administration**

When subjects are dosed at the site or at their home, they will receive study treatment directly from the investigator or designee which may include a study nurse. The date and time of each dose administered in the clinic or at the subjects home will be recorded in the source documents.

## **6.6. Treatment of Study Treatment Overdose**

For this study, any dose of GSK2646264 that is above the intended dose is considered an overdose.

GSK does not recommend specific treatment for an overdose. The investigator or physician in charge of the subject at the time will use clinical judgment to treat any overdose.

## **6.7. Treatment after the End of the Study**

Subjects will not receive any additional treatment from GSK after completion of the study because the indication being studied is not life threatening or seriously debilitating and/or other treatment options are available.

The investigator is responsible for ensuring that consideration has been given to the post-study care of the patient's medical condition, whether or not GSK is providing specific post-study treatment.

## **6.8. Lifestyle and/or Dietary Restrictions**

### **6.8.1. Contraception Requirements**

Contraception requirements are presented in detail in Section [12.4](#)

### **6.8.2. Meals and Dietary Restrictions**

- Refrain from consumption of red wine, Seville oranges, grapefruit or grapefruit juice and/or pummelos, exotic citrus fruits, grapefruit hybrids or fruit juices from 7 days prior to the first dose of study medication until after the final dose.

### **6.8.3. Caffeine, Alcohol, and Tobacco**

- Alcohol will be allowed but limited to an average weekly intake of <21 units for males or <14 units for females).
- There are no caffeine or tobacco restrictions.

### **6.8.4. Activity**

Subjects will abstain from strenuous exercise for 48 hours prior to each blood collection for clinical laboratory tests. Subjects may participate in light recreational activities during studies.

Subjects should refrain from taking part in water based activities such as swimming and use of sauna/steam room for up to 3 hours following application of the study drug.

Showers/bathing should not be taken up to 3 hours following application of the study drug.

Use of sunscreen (UVA/UVB protection cream) on any PV lesions or lesions treated with study drug or placebo should be avoided.

## **6.9. Concomitant Medications and Non-Drug Therapies**

### **6.9.1. Permitted Medications and Non-Drug Therapies**

See Section [5.1](#) for complete details of permitted medications.

### 6.9.2. Prohibited Medications and Non-Drug Therapies

See Section [5.2](#) for complete details of prohibited medications

## 7. STUDY ASSESSMENTS AND PROCEDURES

Protocol waivers or exemptions are not allowed with the exception of immediate safety concerns. Therefore, adherence to the study design requirements, including those specified in the Time and Events Table, are essential and required for study conduct.

This section lists the procedures and parameters of each planned study assessment. The exact timing of each assessment is listed in the Time and Events Table Section [7.1](#).

The following points must be noted:

- If assessments are scheduled for the same nominal time, THEN the assessments should occur in the following order:
  1. 12-lead ECG
  2. vital signs
  3. blood draws.

Note: The timing of the assessments should allow the blood draw to occur at the exact nominal time.

- The timing and number of planned study assessments, including safety, pharmacokinetic, pharmacodynamic/biomarker or others] assessments may be altered during the course of the study based on newly available data (e.g., to obtain data closer to the time of peak plasma concentrations) to ensure appropriate monitoring.
- The change in timing or addition of time points for any planned study assessments must be documented in a Note to File which is approved by the relevant GSK study team member and then archived in the study sponsor and site study files, but this will not constitute a protocol amendment.
- The IRB/IEC will be informed of any safety issues that require alteration of the safety monitoring scheme or amendment of the Informed Consent Form.
- No more than 450 mL of blood will be collected over the duration of the study, including any extra assessments that may be required.
- Photographs may be taken of some of the procedures, tests, medical condition or reactions which may occur during the study.

